9.2.2 Contact Lens care

OPTI-FREE® PureMoist® multipurpose disinfecting solution and lens cases (Alcon, Fort Worth, TX) will be provided to all subjects for care and maintenance of the contact lenses during the study. The sponsor will be providing the lens care solutions to the sites. Subjects will be provided with written instructions on the proper use of this product to clean and disinfect their contact lenses (App 19, Package insert for OPTI-FREE® PureMoist® multipurpose disinfecting solution).

9.2.3 Rewetting/ lubricating eye drops

Subjects will be asked not to use rewetting/ lubricating eye drops during the study.

9.2.4 Storage of Study Medications/Treatments

There are no unapproved investigational products, medications or treatments used in this study requiring special storage accommodations. Room temperature storage is recommended for all study products.

9.2.5 Clinical Supply Inventory

There are no unapproved investigational products used in this study requiring special inventory requirements. Study product will be accounted for using the product accountability forms provided to each site by CooperVision.

9.2.6 Disposal of Consumables

This study dispenses consumables (lenses and lens care product) to subjects for use over 2 months during the study. All study lenses worn by subjects will be collected at their 1 month of wear, respectively. All unused lens care will also be collected and disposed of at the site. Please refer to App 23 for instructions.

9.2.7 Masking and Control of Study Materials

The study contact lenses will be **masked to the subject** only. Study lenses will be inserted from the blister pack after the foil has been removed and transfer to a lens case by the investigators/ assistant to aid masking. The investigator will not be masked.

9.2.8 Ordering and Accountability of Study Materials

The study lenses and solutions will be provided by the sponsor. If additional lenses are required, the study sponsor will re-supply the investigator as requested. The sites are responsible for completing accountability logs for lens dispenses.

9.3 Visit Schedule and Procedures

The visit schedule is shown in Table 2 below.

Table 2: Visit schedule

Visit code	Visit schedule	Visit Description
1	—	Screening and establish optimum prescription with Avaira Toric lenses.
2	1 to 2 weeks from Visit 1*	Dispense new or modified power Avaira Toric (scheduled when lenses are available)*
3	Greater than 28 days from V2 **	1-month Baseline Data collection wearing Avaira Toric AND dispense Avaira Vitality Toric**
4	2-weeks from Visit 3 (12-16 Days from V3)	2-week progress visit with Avaira Vitality Toric
5	1 month from Visit 3 (27-32 Days from V3)	1-month progress visit with Avaira Vitality Toric AND Study exit

**Note: Visit 2 is only necessary if a change in Avaira Toric power is required, or if a refit into Avaira Toric is required for adaptation*

***Note: This visit will be scheduled when Avaira Vitality Toric lenses are available to be dispensed*

The forms that need to be completed at each visit is outlined in Table below:

Table 2: Study Forms

Forms	Visit 1 / 1R	Visit 2 / 2R	Visit 3	Visit 4	Visit 5
Informed Consent Letter	X				
Inclusion/Exclusion	X				
Avaira Vitality Prescription Form	X*	X			
Avaira Toric Prescription Form	X**	X			
Biomicroscopy	X	X	X	X	X
Avaira Toric Dispense		X			
Avaira Toric Re-Dispense		X			
Baseline Avaira Toric			X		
Avaira Vitality Toric Dispense			X		
2W Avaira Vitality Toric				X	
1M Avaira Vitality Toric					X
Appendix 8 Subjective Assessment			X	X	X
Appendix 25 Subjective Assessment Insertion			X		
Appendix 9 Agreement questionnaire			X	X	X
Appendix 11 Lens Preference questionnaire				X	X
Investigator's preference			X	X	X

**Note: Avaira Vitality Prescription Form will be completed at V1 ONLY for those subjects that are current Avaira Toric wearers and do not require a change in prescription*

***Note: Contact Lens Order Form will be completed at V1 ONLY for those subjects that require fit into new or modified Avaira Toric lenses*

[figure not shown]
9.3.1 Visit 1: Screening visit & Establish Optimum Prescription

This visit will be performed to assess eligibility and to establish optimum prescription. The subjects should attend the first visit wearing their habitual lenses and having worn them that day for at least 2

hours prior to the visit. If they are not wearing their lenses, please reschedule the visit. The following baseline measurements and assessments will be recorded:

- The subject will be required to read and sign an Informed Consent Form prior to enrolment (App 18). When the subject has signed the consent form, the subject will be considered to be enrolled on to the study.
- The person explaining the consent/ the Investigator should also sign the consent form.
- The subject will be provided with a copy of the consent and the original will be kept in the subject's paper chart. It may also be scanned into the subject's electronic medical record (EMR) file.
- The subject is assigned with a Subject ID number. Subjects must be enrolled sequentially.
- The subject enrollment log will be updated (App 20).
- Screening Form (App 1) will be completed to assess eligibility with respect to habitual lens wear, ocular and medical history.
- Subject's age and gender
- Details of current lens:
 - Brand
 - Power(s)
 - Replacement schedule
 - Lens age (days)
- Current lens care used
- Use of rewetting/lubricating drops
- Habitual lens wearing times:
 - Average daily wearing time (hours/day)
 - Average comfortable wearing time (hours/day)
 - Number of days/week (lenses are worn).
- Health history and medications
- Overall habitual lens fit acceptance (0 - 4) and reason if Grade 2 or less and lens orientation
- Habitual high contrast, distance monocular Snellen visual acuity
- Habitual high contrast, distance binocular Snellen visual acuity
- Over-refraction with habitual lenses and Snellen visual acuity with over-refraction
- Remove habitual lenses.
- Automated refraction including keratometry readings
- Subjective sphero-cylindrical refraction and high contrast monocular and binocular Snellen visual acuity
- Determine if subjects need to be scheduled for Visit 2 or Visit 3:
 - For a subject who is a current Avaira Toric wearer and does not require a change in prescription, please complete Avaira Vitality Prescription Form (App 3). Subject can be scheduled for Visit 3 when Avaira Vitality Lenses are available (≥ 29 days after screening visit 1).

- For a subject who is a current Avaira Toric wearer but requires a change in prescription, please complete Avaira Toric Prescription Form (App 2B) and schedule Visit 2.
- For a subject who is not a current Avaira Toric wearer, please complete Trial Lens Fitting Form (App 2A) and fit lenses accordingly, after the trial lens fit was successful, complete Avaira Toric Prescription Form (App 2B) and schedule Visit 2.

- Anterior segment ocular health will be assessment (App 4)
 - External Adnexa anomalies (Present/Absent & Describe)
 - Hyperemia
 - Bulbar (0-4, 0.5 steps)
 - Limbal (0-4, 0.5 steps)
 - Palpebral (0-4, 0.5 steps)
 - Cornea & Anterior eye
 - Infiltrates (0- 4, 1 step)
 - Conjunctival infection (0-4, 1 step)
 - EKC (0-4, 1 step)
 - Corneal ulcers (0-4, 1 step)
 - Lens Adhesions (0-4, 1 step)
 - Recurrent Erosions (0-4, 1 step)
 - Other abnormalities (0-4, 1 step)
 - Staining
 - Corneal Staining (0-4, 0.5 step & Optional sketch of staining)
 - Conjunctival Staining (0-4, 0.5 step)
 - Conjunctival Indentation (0-4, 0.5 step)
 - Other findings
- Eligibility Checklist (App 5) will be completed
- Complete Enrolment Log (App 20). If at this point the subject is found to be ineligible, then complete an Exit form (App 13) and exit the subject from the study.

- If a subject is a current Avaira Toric lens wearer and no change to the lens prescription is required then the subject will be instructed to wear the lenses on a daily wear basis, (at least 5 days/week, >8 hours/day), until Visit 3 appointment can be scheduled, unless they experience a problem which warrants lens removal.
- If a subject requires a new prescription for Avaira Toric lenses, please complete the Avaira Toric Prescription Form (App 2B), order the lenses and schedule Visit 2
- If a subject is not a habitual Avaira Toric wearer, re-fit subject into Avaira Toric lens using the Trial Lens Fitting Form (App 2A). After the fit was successful, please complete the Avaira Toric Prescription Form (App 2B), order the lenses and schedule Visit 2.

In some circumstances a repeated Screening may need to be scheduled. Examples include, but are not limited to:

1. Study procedures unable to be completed in time scheduled for visit;
2. Study products not available at the time of the study visit;
3. A transient health condition which may affect the eye(s) (e.g. a common cold, active allergies, fatigue etc.);
4. The short term use of medications (e.g. antibiotics, antihistamines etc.);
5. Reassessment of ocular conditions (e.g. corneal and/or conjunctival staining, scars etc.).

The maximum total number of repeat screenings permitted will be one (App1R)

9.3.2 Visit 2: Dispense of Avaira Toric Lens

If this visit is required, it will be scheduled when the Avaira Toric lenses are available. This visit will be performed to fit and dispense new or modified power Avaira Toric lenses. Hence, this visit is only necessary if a change in Avaira Toric power is required or if a re-fit into Avaira Toric is required for adaptation. The following measurements and assessments will be recorded:

- Ensure no changes to health/medications and no contraindications for lens wear (App 6A)
- Complete biomicroscopy (App 4)
- A minimum 5 minute washout time after fluorescein insertion is required prior to lens insertion. The performance of the lenses should be assessed after 10-15 minutes settling time. The following variables will be assessed (App 6A)
- Record the parameters of the lenses, lot number, and power, on the Dispensing CRF
- Vision
 - High contrast distance monocular Snellen visual acuity
 - High contrast distance binocular Snellen visual acuity
- Over- refraction and Snellen visual acuity with over-refraction
 - Amendments to the distance sphere power, cylindrical power and/or axis can be made. Record the number of trial lenses required to achieve a successful fit

- Overall lens fit acceptance (0-4) and reason if Grade 2 or less and record lens orientation
- To be successfully dispensed, subjects must show \geq Grade 2 lens fit acceptance with the trial fit lens and must be correctable to 20/30 (0.18 logMAR) or better in each eye with the study contact lenses.
- If the lenses are not a suitable fit to be dispensed then the subject will be discontinued and an Exit Form (App 13) will be completed.
- If successful lens fit and no lens modification is needed, then complete Avaira Vitality Prescription Form (App 3)
- The subject will be instructed to wear the lenses on a daily wear basis, (at least 5 days/week, >8 hours/day), until Visit 3 appointment, unless they experience a problem which warrants lens removal.
- The Investigator or a clinical assistant will review instructions and warnings for lens wear and care, when to remove lenses, and other important issues with the subject.
- Subjects, who appear unable or unwilling to follow instructions to a degree that, in the Investigator's opinion, jeopardizes the subject's wellbeing or the validity of the study, will be discontinued. The reason for discontinuation will be documented.

In some circumstances a repeated Dispensing visit (Visit 2R) may need to be scheduled if an over-refraction was found and lenses in a different prescription need to be ordered. The maximum total number of repeat dispense visit permitted will be one (App 2R)

9.3.3 Visit 3: Baseline with Avaira Toric & Dispense of Avaira Vitality Toric lenses

- If subject is an habitual Avaira Toric wearer with optimum prescription then Visit 3 will be scheduled at least 29 days after **Visit 1**
- If subject was fit into new or modified Avaira Toric lenses then Visit 3 will be scheduled at least 29 days after **Visit 2**
- The subject should wear the lenses for a minimum of 2 hours prior to the appointment. If the subject attends without lenses or with less than 2 hours of lens wear on that day and they are not having any problems with their lenses, the visit should be rescheduled, if possible within the visit window. The following clinical test variables will be recorded on the CRFs as indicated:

Visit 3a: Baseline for Avaira Toric Lenses (App 7A)

- Confirm if any changes to health or medications
- [REDACTED]

[REDACTED]

[REDACTED]

[REDACTED]

[REDACTED]

[REDACTED]

- [REDACTED]
- Vision
 - High contrast distance monocular Snellen visual acuity
 - High contrast distance binocular Snellen visual acuity
- [REDACTED]
- Lens fit
 - Lens centration (centered/slightly decentered/substantially decentered)
 - Corneal coverage [Y/N]
 - [REDACTED]
 - Post-blink movement (0-4 Likert scale)
 - [REDACTED]
 - [REDACTED]
 - [REDACTED]
 - [REDACTED]
 - Overall fit acceptance (0 - 4) and reason if Grade 2 or less 1 step.
- Remove study lenses and perform slit lamp examination. A minimum 5 minute washout time after fluorescein insertion is required prior to lens insertion.

Visit 3b: Fitting and Dispensing of Avaira Vitality Toric Lens (App 7B)

The performance of the lenses should be assessed after 10-15 minutes settling time and the following variables will be assessed:

- Record the parameters of the lenses, lot number, and power, on the Dispensing CRF (App 7B).
- Vision
 - High contrast distance monocular Snellen visual acuity
 - High contrast distance binocular Snellen visual acuity
- [REDACTED]
- [REDACTED]
- [REDACTED]
- Lens fit
 - Lens centration (centered/slightly decentered/substantially decentered)
 - Corneal coverage [Y/N]
 - [REDACTED]

– Post-blink movement (0-4 Likert scale)

– [REDACTED]
[REDACTED]
[REDACTED]
[REDACTED]
[REDACTED]

– Overall fit acceptance (0 - 4) and reason if Grade 2 or less.

- [REDACTED]
[REDACTED]
[REDACTED]
[REDACTED]
[REDACTED]
[REDACTED]

- To be successfully dispensed, subjects must show >Grade 2 lens fit acceptance with the trial fit lens and must be correctable to 20/30 (0.18 logMAR) or better in each eye with the study contact lenses.
- If the lenses are not a suitable fit to be dispensed then the subject will be discontinued and an Exit Form (App 13) will be completed.
- The subject will be instructed to wear the lenses on a daily wear basis, (at least 5 days/week, >8 hours/day), until Visit 4 appointment, unless they experience a problem which warrants lens removal.
- The Investigator or a clinical assistant will review instructions and warnings for lens wear and care, when to remove lenses, and other important issues with the subject.
- Subjects, who appear unable or unwilling to follow instructions to a degree that, in the Investigator's opinion, jeopardizes the subject's wellbeing or the validity of the study, will be discontinued. The reason for discontinuation will be documented.
- The subject will be discharged and asked to return for a follow-up visit (V4) after 2-weeks

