3.1 Study Hypothesis

- Null hypothesis (Ho): There is no difference in lens performance between Enfilcon A toric and Fanfilcon A toric lenses for the key variables measured.
- Alternative hypothesis (H1): There is a difference in lens performance between Enfilcon A toric and Fanfilcon A toric lenses for the key variables measured.

4 Study Design

This is a prospective, multi-center, subject-masked, bilateral wear, two month dispensing study comparing the clinical performance of the Fanfilcon A toric lenses following a refit and adaptation with Enfilcon A toric lenses (Table 1). The subjects will be fit bilaterally into the Enfilcon A toric lenses at the first visit (or continue wearing their habitual Enfilcon A toric lenses) which will be worn for a minimum of one month and then subjects will be re-fit bilaterally with a pair of Fanfilcon A toric lenses for another month of daily wear. After the dispensing Fanfilcon A toric lens, subjects will return for follow up evaluations after 2 weeks, and 1 month.

The subjects will be advised that they may be dispensed with either Enfilcon A toric lenses OR Fanfilcon A toric lenses, however all subjects will be refit with Fanfilcon A toric lenses. The participant will not be informed on which study lens he/she is wearing during the second month but the investigator will have this information.

5 Study Population

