9.2 Study Materials

9.2.1 Contact lens

All subjects will have worn, or be fit with an optimized prescription in Avaira Toric for at least one month before being fit and dispensed the Avaira Vitality Toric. Details of the contact lenses are shown in Table 1.

The Avaira Vitality Toric lenses will be provided by the Sponsor. The sites may be asked to source the Avaira Toric lenses as needed and retain invoices for reimbursement.

Table1: Study lenses

Brand	Avaira Toric lenses (Control)	Avaira Vitality lenses (Test)
Manufacturer	CooperVision	CooperVision
Material	Enfilcon A	Fanfilcon A
Water Content	46%	55%
Base Curve	8.5	8.4
Lens Diameter	14.5	14.2
Lens Powers Sphere	-1.00 to - 6.00 (0.25 steps)	-1.00 to - 6.00 (0.25 steps)
Lens Power Cylinder	-0.75, -1.25, -1.75	-0.75, -1.25, -1.75
Axis	10 ^o to 180 ^o (10 ^o steps)	10 ^o to 180 ^o (10 ^o steps)
Replacement schedule	Daily wear	Daily wear

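### The minimum interval to the Visit 3a control baseline is counted from Visit 2 even when the final Avaira Toric prescription is first dispensed at Visit 2R, so the schedule permits less than the month in an optimised prescription that section 9.2.1 requires

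*Combined protocol and SAP*

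**What the plan says.** **Wear requirement.** Section 9.2.1: "All subjects will have worn, or be fit with an optimized prescription in Avaira Toric for at least one month before" the test lens is dispensed. Section 4 says of the Enfilcon A toric lenses, "which will be worn for a minimum of one month and then subjects will be re-fit bilaterally" with the test lens; it does not mention optimisation. The study title and section 9.1 likewise set a one-month minimum in Avaira Toric without referring to the final power.

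**Timing rule.** Table 2 in section 9.3 places Visit 3 at "Greater than 28 days from V2". Section 9.3.3 distinguishes two groups. Habitual Avaira Toric wearers already in their optimum prescription are counted from Visit 1. For subjects fitted with "new or modified Avaira Toric lenses then Visit 3 will be scheduled at least 29 days after Visit 2", the count starts at Visit 2. A footnote to Table 2 adds that Visit 3 waits until the Avaira Vitality Toric lenses are available.

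**Repeat dispensing.** The end of section 9.3.2 provides that one "repeated Dispensing visit (Visit 2R) may need to be scheduled if an over-refraction was found and lenses in a different prescription" have to be ordered, and that "The maximum total number of repeat dispense visit permitted will be one". No interval from Visit 2 to Visit 2R is given, and neither timing rule names Visit 2R.

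**Test-lens exposure.** Table 2 sets Visit 5 at 27 to 32 days from Visit 3.

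**The concern.** Visit 2R exists for subjects whose Visit 2 lenses proved not to be the final prescription. For them the optimised lens is first dispensed at Visit 2R, but the minimum interval has been running since Visit 2. The scheduling rule thus permits what section 9.2.1 does not.

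Visit 3a is the only visible control-lens assessment scheduled after a month of wear, and it supplies the control side of the paired comparisons in section 11.1. For Visit 2R subjects, exposure to the final control lens could be shorter than exposure to the test lens at Visit 5. There is no randomised order or second control period to balance the difference.

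The shortfall would also be hard to see afterwards. A Visit 3 held 29 days after Visit 2 complies with the schedule, so its date would not flag a deviation for the cohort discussion in section 12.1. Section 11.1 keeps all evaluated subjects in the analysis.

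**Working it through.** **Inputs from the documents**
- Minimum interval, Visit 2 to Visit 3: 29 days (section 9.3.3). In whole days this equals Table 2's limit of more than 28 days, so the two rules agree with each other.
- Visit 1 to Visit 2: 1 to 2 weeks, scheduled when lenses are available (Table 2).
- Test-lens wear at Visit 5: 27 to 32 days (Table 2).
- Repeat dispensing visits: at most one (section 9.3.2).

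**Assumption.** The gap g from Visit 2 to Visit 2R is not stated. Since lenses must again be ordered, the 1 to 2 weeks for Visit 1 to Visit 2 serves as a proxy: g = 7 to 14 days. Other values are shown for range.

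**Formula.** Wear in the final prescription at the earliest permitted Visit 3 = 29 − g; shortfall = g/29.

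| g (days) | Wear in final prescription (days) | Shortfall |
|---|---|---|
| 3 | 29 − 3 = 26 | 3/29 = 10% |
| 7 | 29 − 7 = 22 | 7/29 = 24% |
| 10 | 29 − 10 = 19 | 10/29 = 34% |
| 14 | 29 − 14 = 15 | 14/29 = 48% |
| 21 | 29 − 21 = 8 | 21/29 = 72% |

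Any gap of a day or more falls below 29 days; only the size depends on the assumption. Under the proxy, wear is 15 to 22 days. That is 27 − 22 = 5 to 32 − 15 = 17 days less than test-lens wear at Visit 5.

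**Does waiting for the test lenses close the gap?** Under section 9.3.2 the Avaira Vitality prescription form is completed once the fit succeeds and no modification is needed, which for these subjects is in effect at Visit 2R. If supply then takes another 7 to 14 days (again an assumption), the test lenses arrive 7 + 7 = 14 to 14 + 14 = 28 days after Visit 2. That is before day 29, so the condition need not delay Visit 3.

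**After re-anchoring.** Every Visit 2R subject has at least 29 days in the final prescription. The earliest Visit 3 moves to 29 + 7 = 36 to 29 + 14 = 43 days after Visit 2.

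**Sample size.** The figure in section 5.1 reproduces and does not depend on this point. A two-sided paired t-test with the SD of 2.4 read as that of the paired differences, alpha 0.05 and a difference of 1.04 gives n = 44, with power 0.802.

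**The case against.** **Visit 2 may be meant to include its repeat.** Visit 2R is described as a repeated dispensing visit, and the forms table puts both under one column. That reading is open. However, the protocol labels Visit 2R separately and lists separate dispense and re-dispense forms, while the timing rules name only Visit 2. Four sites could read this differently. The appendix forms are not part of the document, so an instruction there cannot be excluded.

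**The 29 days is a floor with no upper limit.** A site can satisfy both sections by scheduling later, and nothing directs it to go early. This stands: the fault lies in what the rule permits. But the floor is what guarantees the minimum, and for these subjects it does not.

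**Only section 9.2.1 speaks of an optimised prescription.** This also stands. A reader might infer that the title and section 4 demand a month in the final power, or that Visit 2R subjects are not adapted Enfilcon A toric wearers. Neither follows: a habitual Avaira Toric wearer whose power changes can still meet the general one-month wording. Against that, section 9.3.3 itself moves the start from Visit 1 to Visit 2 when the power is modified, so the plan does treat a new power as restarting the count.

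**Effect on results.** A reader might infer that the control lens is handicapped because subjects spent time in a wrong power. The documents do not say what is worn between Visit 2 and Visit 2R. At Visit 3a, vision and fit are measured in the final lens. Fit and acuity are also assessed 10 to 15 minutes after insertion at dispensing, and the test lens has a planned assessment at 12 to 16 days. Nothing in the documents shows that 15 to 22 days rather than 29 changes these outcomes.

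**Conclusion.** The conflict is real but narrow. Section 9.2.1 sets a minimum time in an optimised Avaira Toric prescription, and Table 2 and section 9.3.3 start the count at a visit where, for Visit 2R subjects, that prescription had not yet been dispensed. A site following the schedule could hold Visit 3a with 15 to 22 days in the final prescription, if the unstated gap is 1 to 2 weeks.

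The number of subjects needing Visit 2R is not given. It may be small, since subjects new to Avaira Toric have a successful trial fit at Visit 1 before lenses are ordered and some habitual wearers skip Visit 2. Each affected subject is 1/44 = 2.3% of the target analysis cohort.

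Two stronger conclusions are not supported. Visit 3a is not the only control-lens measurement: where Visit 2 is held, acuity and fit acceptance in Avaira Toric are recorded there, though without a month of wear. Nor is a bias against the control shown; its direction and size are not established.

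**What to change.** Reconcile section 9.2.1, Table 2 and section 9.3.3 so that the existing minimum interval to Visit 3 is counted from the visit at which the final-prescription Avaira Toric was dispensed: Visit 2, or Visit 2R if held. No new interval is needed. The edit is one clause in Table 2 and the same clause in section 9.3.3.

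The cost is a later Visit 3 for Visit 2R subjects only, by the length of their gap between Visit 2 and Visit 2R (7 to 14 days under the assumption above). The sample size and the analysis methods stay as they are.
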